# 7 Sample Size

(ICH E3; 9.7.2. ICH E9; 3.5)

The sample size is n = 100 randomized participants. In order to be randomized, participants must complete baseline assessments.

# 8 General Analysis Considerations

### 8.1 Timing of Analyses

Final analyses will be performed when data collection is completed. In particular, the final analyses will be performed when all enrolled study subjects have completed the 24-week follow up timepoint or dropped out prior to the 24-week timepoint. The final analysis will be performed on data transferred to a file from REDCap, having been documented as meeting the cleaning and approval requirements after the finalization and approval of this SAP document. Data cleaning will involve checking REDCap surveys for errors/discrepancies, ensuring all responses are correctly scored REDCap, and then performing a quality check to ensure answers were scored accurately. For the ActiGraph, we will ensure data was recorded at 60Hz, that data fell within the expected wear time range, and that included participants met our wear time criteria of at least 4 days and at least 10 hours on those days. As well, we will cross-reference the date the monitor was worn from the Actigraph is between the dates the monitor was send the received from REDCap. We will also check that the file names and dates of the Actigraph files correspond to names and dates from REDCap.

### 8.2 Analysis Populations

(ICH E3; 9.7.1, 11.4.2.5. ICH E9; 5.2)

#### 8.2.1 Full Analysis Sample (Intention to Treat)

- All subjects who were randomized
- This will be the primary efficacy sample

#### 8.2.2 Per Protocol Sample

- Of those in the Full Analysis sample in 8.2.1, we will include all subjects who adhere to the major criteria in the protocol
  - o Completed their respective intervention group
    - For Intervention group  $\geq$  3 of 5 consultations
    - For Control group, accessed the website.

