Treatment Expectations Question: The participant will complete a Treatment Expectations Question, which asks the participant how effective they expect the intervention to be for their knee. This question will be collected at the baseline timepoint: right before and right after

randomization. Answers will be expressed as frequencies and percentages for each of the following categories: No effect at all, Minimal improvement, Moderate improvement, Large improvement, and Complete recovery, as well as reported as an increase, decrease, or no change in treatment expectations.

Exercise Adherence: For the Expanded Intervention, adherence to strengthening exercises and physical activity will be measured using the Exercise Adherence Rating Scale (EARS). The EARS includes 6 items whose total score ranges from 0 to 24, where a higher score indicates greater adherence. The EARS also includes 10 items on what helps or hinders exercise adherence. These scores range from 0 to 40, where a higher score indicates better outcome.

Brief Intervention Utilization: For the Brief Intervention, intervention utilization will be measured via a self-report questionnaire administered on REDCap. The participant will be asked to confirm that they viewed the informational videos, accessed the associated weblink, and note how many times they visited the site for each webpage section. Percentage of Brief Intervention participants that utilize the website will be reported. Utilization of the Brief Intervention will be measured at the 12-week follow-up timepoint.

Adverse Events (AE): Information on potential adverse events (AE) will be collected by the treating physical therapist at the beginning of each session in the Expanded Intervention, by a Research Assistant during follow-up reminder phone calls in the Brief Intervention, or by spontaneous report on the part of the participant (e.g., reaching out to the study team by phone or email). AEs will be reported as frequencies and percentages.

General Information Form: The participant will complete a General Information Form that collects height, weight, date of birth, gender, race, ethnicity, veteran status, highest level of education attained, employment status, and approximate household income. This form will be collected at the baseline timepoint. Continuous variables will be expressed as means and standard deviations while categorical variables will be expressed as frequencies and percentages.

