8.2.1 Full Analysis Sample (Intention to Treat)

- All subjects who were randomized
- The ActiGraph monitor was worn for > 4 days of 10 hours at the baseline and 12week follow-up timepoints
- This sample will be the primary efficacy sample

8.2.2 Per Protocol Sample, set 1

All subjects who adhere to the major criteria in the protocol
Subjects who did not drop out

- Completed their respective intervention, (60% of Intervention)
- Did not drop out over the 12 weeks of follow up after the intervention
- The ActiGraph monitor was worn > 4 days at each time point (baseline and 12-week follow-up timepoints).

8.2.3 Per Protocol Sample, set 2

- All subjects who adhere to the major criteria in the protocol
 - o Subjects who did not drop out
 - Completed their respective intervention (60% of Intervention)
 - Did not drop out over the 24 weeks of follow up after the intervention
 - The ActiGraph monitor was worn > 4 days at each time point (baseline, 12week, 24-week follow-up timepoints).

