#### 8.2.3 Secondary Data Analysis Sample

• We will repeat the Per Protocol analysis for outcomes measured with the ActiGraph excluding participants on those who worn their ActiGraph monitor outside of our established visit windows.

The exact process for assigning the statuses (Full Analysis Sample and Per Protocol

Sample) will be defined and documented prior to breaking the blind along with any predefined reasons for eliminating a subject from a particular population.

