#### **Treatment Compliance**

#### Table 6: Treatment Compliance Measures

Table 0. Treatment Compliance Measures	Control		
	-	Intervention	
Number of physical therapy consultations (0-5), mean (SD)	_		
Number of physical therapist consultations, n (%)			
0	-		
1	-		
2	-		
3	-		
4	-		
5	-		
Duration of physical therapist consultations (mins), mean (SD)			
Initial	-		
Follow-ups	-		
PT discussed steps/day n/N (%)			
1 st consultation	-		
2 nd consultation	-		
3 rd consultation	-		
4 th consultation	-		
5 th consultation	-		
PT discussed step goals n/N (%)			
1 st consultation	-		
2 nd consultation	-		
3 rd consultation	-		
4 th consultation	-		
5 th consultation	-		
Self-reported adherence to exercises (EARS) 			
12 weeks	-		
24 weeks	-		
Website access, n/N (%)			
Never		-	
> 1 visit		-	

<sup>1 EARS (Exercise Adherence Rating Scale) range 0-24 with higher scores representing more adherence. SAP version 1.2: Delaware PEAK3/1/24 Page 20 of 38

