### 9.6 Secondary Efficacy Analyses

#### 9.6.1 Secondary Analyses of Primary Efficacy Endpoint

The per protocol sample, instead of the ITT sample will be used for the analysis of the primary efficacy endpoint.

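### The per-protocol sample filters the two arms with different post-randomisation tests and no correction, so its contrast may be biased in a direction and by an amount the documents do not fix

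*SAP*

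**What the plan says.** SAP 8.2.2 takes the per-protocol sample from the full analysis sample by whether participants completed their assigned arm. In the intervention arm this means at least "3 of 5 consultations", which SAP Table 1 spreads over weeks 1 to 10. In the control arm the rule is "For Control group, accessed the website". SAP Table 6 shows how low that bar is: the row "Website access, n/N" has only two levels, never and one or more visits. Protocol 8.2.2 words the rule identically for both arms: "Completed their respective intervention, (60% of Intervention").

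On the source of the control data, Protocol 6.4 says "intervention utilization will be measured via a self-report questionnaire administered on REDCap" and "Utilization of the Brief Intervention will be measured at the 12-week follow-up timepoint". SAP v1.2 has no such paragraph and does not say how or when access is established.

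The sample is used widely. SAP 9.6.1 states: "The per protocol sample, instead of the ITT sample will be used for the analysis of the primary efficacy endpoint". SAP 9.6.2 and 9.7 add separate per-protocol analyses of the secondary outcomes, VAS pain and the KOOS subscales. SAP 8.2.3 makes this sample the base for the visit-window check: "We will repeat the Per Protocol analysis for outcomes measured with the ActiGraph", leaving out monitors worn outside the window. SAP 8.2.1 keeps the full analysis sample as primary.

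**The concern.** Attending three consultations takes sustained engagement; opening a website once does not. If engagement also predicts change in MVPA, the people kept in the two arms differ in a way that randomisation no longer balances, and the per-protocol difference mixes any treatment effect with that selection. SAP 8.3 picks covariates from baseline demographic differences, which does not address selection on later behaviour.

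Two results are at stake. A per-protocol estimate printed beside ITT for almost every outcome invites being read as confirmation or contradiction, and it can reliably serve as neither. In addition, SAP 6.4 keeps out-of-window data in the primary analyses and promises an analysis without them, yet 8.2.3 runs that exclusion only inside the selected subset. A change in the result could then come from visit timing or from adherence selection, and the reader could not tell which.

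**Working it through.** **1. The plan's own figures.** The only sample-size figure is n = 100 (SAP section 7). No effect size, SD, power, dropout or expected per-protocol share is given, so 100 cannot be reproduced. The intervention rule does match the Protocol's percentage: 3/5 = 0.60.

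**2. Scale.** Assume 1:1 allocation (50 per arm; the ratio is not stated) and two-sided alpha 0.05 (not stated; inferred from the 95% intervals). The difference detectable with 80% power and no dropout is (1.960 + 0.842) × √(2/50) = 0.56 SD.

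**3. Null model.** Change in MVPA has the same distribution in both arms. A latent trait with correlation ρ to change decides who passes, and the top share p of each arm is kept. The mean trait among those kept is λ(p) = φ(z)/p, where z is the normal quantile that cuts off the top p. Then

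bias (SD of change) = ρ_I × λ(p_I) − ρ_C × λ(p_C).

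The values needed are λ(0.95) = 0.10314/0.95 = 0.1086, λ(0.80) = 0.27996/0.80 = 0.3500, λ(0.70) = 0.34769/0.70 = 0.4967 and λ(0.60) = 0.38634/0.60 = 0.6439.

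Two worked cases:
- 60% versus 95% passing, ρ = 0.5: 0.5 × (0.6439 − 0.1086) = +0.268.
- 95% versus 70% passing, ρ = 0.5: 0.5 × (0.1086 − 0.4967) = −0.194.

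**4. Results.** All pass rates and correlations are assumptions. Type I error is from simulation with 50 randomised per arm, a t-test on change and 8,000 runs per row, so its Monte Carlo error near 5% is about √(0.05 × 0.95/8000) = 0.24 percentage points.

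| Intervention pass | Control pass | ρ_I / ρ_C | Bias (SD) | Type I error |
|---|---|---|---|---|
| 80% | 80% | 0.3 / 0.3 | 0.000 | 5.1% |
| 80% | 95% | 0 / 0 | 0.000 | 4.6% |
| 80% | 95% | 0.3 / 0.3 | +0.072 | 6.2% |
| 80% | 95% | 0.5 / 0.5 | +0.121 | 8.6% |
| 60% | 95% | 0.3 / 0.3 | +0.161 | 10.1% |
| 60% | 95% | 0.5 / 0.5 | +0.268 | 22.2% |
| 95% | 80% | 0.3 / 0.3 | −0.072 | 6.1% |
| 95% | 70% | 0.5 / 0.5 | −0.194 | 14.3% |
| 80% | 80% | 0.1 / 0.4 | −0.105 | 7.4% |

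**5. Reading.** The bias is positive when the consultation test removes more of the people who would have changed least. It turns negative when more controls fail, for example if a missing 12-week report counts as no access, or when passing the control test predicts change more strongly. The last row shows that equal pass rates alone do not remove it.

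**The case against.** A reader might infer that the higher bar in the intervention arm must make the per-protocol contrast favour the intervention. The documents do not support that. They give no pass rates, dropout or correlation, and the reporting route in the Protocol pushes the other way: if access is known only from a 12-week self-report, controls who leave early cannot qualify, which lowers the control pass rate. A reader might also take that self-report as the SAP's current source, but the SAP does not say so.

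Other points against the concern carry weight:
- ITT is primary, and no confirmatory claim rests on the per-protocol sample.
- The largest positive figures need 40% of the intervention arm to fail, which nothing in the documents suggests.
- The early-dropout asymmetry matters little for the primary endpoint. An intervention participant who attends three sessions and leaves before week 12 has no 12-week MVPA and adds little to the contrast.
- SAP 8.2.3 promises to document how sample status is assigned before unblinding, and Supplemental Table 1 will show per-protocol demographics by arm.
- A complier-average effect is a different estimand with its own assumption. Applied to everything it would mean 13 outcomes (MVPA, LPA, steps, four TOA scores, VAS, five KOOS subscales).
- Restricting the visit-window check to the per-protocol sample was a deliberate, logged change in v1.1.

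These points limit the reach of the problem without removing it. Documenting the assignment process could settle the data source, but it would not make two different tests comparable. Supplemental Table 1 does not list MVPA, and balance on demographics does not establish balance on motivation. That the visit-window restriction was deliberate does not give the reader a check that keeps the randomised groups.

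**Conclusion.** The per-protocol rule applies unequal post-randomisation filters, and nothing planned corrects for the selection. The resulting contrast may be biased under no effect. Bias towards the intervention is plausible, because one website visit is easier to achieve than three consultations, but neither sign nor size is established. In the scenarios tried it runs from about −0.19 to +0.27 SD against a detectable difference of 0.56 SD. These are illustrations resting on assumed pass rates, correlations, 1:1 allocation and alpha 0.05; they are not limits. If passing is unrelated to change in MVPA, the bias is zero.

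The damage is confined to secondary, exploratory and sensitivity results; the primary ITT conclusion stands. The unstated source of website access in the current SAP is a further, smaller gap, since that variable decides which controls are included.

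**What to change.** 1. **SAP 8.2.3:** also run the out-of-window exclusion in the full analysis sample, so that the check promised in 6.4 starts from the randomised groups. This needs one sentence and one repeat of the ActiGraph models. The same edit should reconcile 9.2, which treats out-of-window follow-ups as missing, with 6.4, which keeps them.
2. **SAP 9.6.1:** for MVPA at least, make the adherence-adjusted estimate a complier-average effect in the full analysis sample, with randomisation as instrument and receipt defined as at least 3 of 5 consultations. It needs no control-arm filter, because controls are assigned web resources only. State two costs beside it. The simple ratio estimate divides the ITT difference by the share receiving treatment, so treating that share as known the interval widens by about 1/0.80 = 1.25 if 80% qualify, or 1/0.60 = 1.67 if 60% do. It also assumes that one or two consultations have no effect; if they help, the complier effect is overstated.
3. **Per-protocol tables:** label them descriptive, and report pass rates and baseline MVPA by arm. In 8.2.2, name the source and timing of website access and say how a missing report is classified.

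Overall cost: SAP wording, a few extra models and a less precise adherence estimate. No new data collection is needed if website access was recorded as the Protocol describes.

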#### 8.2.3 Secondary Data Analysis Sample

• We will repeat the Per Protocol analysis for outcomes measured with the ActiGraph excluding participants on those who worn their ActiGraph monitor outside of our established visit windows.

The exact process for assigning the statuses (Full Analysis Sample and Per Protocol

Sample) will be defined and documented prior to breaking the blind along with any predefined reasons for eliminating a subject from a particular population.

### 8.3 Covariates and Subgroups

(ICH E3; 9.7.1, 11.4.2.1. ICH E9; 5.7)

Baseline demographics will be assessed for group assignment differences after randomization. Covariates will be determined based on the presence of group differences.

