#### Figure 1: Study flow-chart

### 6.2 Inclusion-Exclusion Criteria and General Study Population

(ICH E3;9.3. ICH E9;2.2.1)

In order to be eligible to participate in this study, an individual must meet all of the following criteria:

- 1. Provision of an electronically signed and dated informed consent form
- 2. >45 years of age,
- 3. Resides in the contiguous United States
- 4. Available for the duration of the intervention portion of the study (12 weeks) and willing to wear physical activity monitors
- 5. Looking to move more, i.e., be more active.
- 6. Knee OA diagnosis by the NICE criteria
- 7. Comfortable participating in a program delivered in English
- 8. Is able to safely participate in moderate-intensity exercise as determined by a preexercise screen questionnaire,
- 9. Has either a smartphone or a laptop/desktop computer with an internet connection.
- 10. Has a working email address.

An individual who meets any of the following criteria will be excluded from participation in this study:

- 1. Regularly exercise for more than 60 minutes/week.
- 2. Has a scheduled knee or hip joint replacement
- 3. Has had physical therapy for knee OA in the past 6 months
- 4. Participated in a strength training program for the lower extremities in the past 6 months

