# 6.3 Randomization and Blinding

(ICH E3; 9.4.3, 9.4.6. ICH E9; 2.3.1, 2.3.2)

Participant-level randomization will be performed to assign each participant to either the Intervention group (referred to as the Intervention) or the Control group using block randomization schedule with block sizes of 4. Randomization was performed using REDCap's built-in randomization function and will occur after participants sign the informed consent and complete baseline data collection. Participants will be randomized into one of two groups: (1) the Intervention group, who will receive the Delaware PEAK program with a physical therapist, or (2) the control group, who will receive pre-recorded, web-based resources.

Participants will not be blinded to group allocation; however, they will not be informed about the study hypotheses until the study is completed, at which time they will be provided a lay summary of findings. The treating physical therapist will not be blinded to group assignment, as they are delivering the Intervention. Research team members responsible for outcome data management will be blinded to group assignment. As all outcomes are collected either through a physical activity monitor or online questionnaires, this study is thus considered assessor-blinded for our primary outcome, physical activity. Statistical analyses will be performed in a blinded manner.

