## 8.4 Missing Data

(ICH E3; 9.7.1, 11.4.2.2. ICH E9;5.3. EMA Guideline on Missing Data in Confirmatory Clinical Trials)

Missing data will be given careful attention in the analysis. In this RCT we have two treatment arms and three fixed times for assessment. It is anticipated that drop-outs from the study will be at random because study participants were considered treatment-seeking. However, it is possible that participants may not attend all follow-ups. Drastically fewer participants in the final analysis would affect study sensitivity and excessive missed follow-ups would potentially bias model parameter estimates. Under the assumption of limited data that is missing completely at random (MCAR) or missing at random (MAR), the mixed-effect model using restricted maximum likelihood estimation is a full information approach and leads to unbiased model parameter estimates. Selection between models with two common covariance structures, Toeplitz and independent errors will be accomplished using the Akaike Information Criterion (AIC).

In the event that assumptions are not met regarding missing value frequency, MAR, or MCAR and missing values are occurring with higher frequency or are truly missing not at random (MNAR), the analysis may be biased. To test the missingness assumptions, missing data will first be summarized by group, time, each design cell, and each of the three covariates, age, sex and body mass index in an effort to graphically or tabularly detect patterns in the variation of missingness. More formally, missing/non-missing will be taken as a dichotomous outcome in a logistic regression for continuous covariates and will be compared with between and within factors and sex using chi-square tests. Significant logistic regression coefficients or significant chi-square tests indicate a pattern of missingness variation that will be identified and reported and whose impact on the analysis will be explained if possible. Model residuals will be evaluated for normality using the Shapiro-Wilk test, homogeneity of variance using Levine's test, and transformations, if necessary, will be chosen from among the Box-Cox transformations.

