### 9.4 Efficacy Analyses

The primary and secondary outcomes will be summarized stratified by treatment group at each study timepoint (baseline, 12-week, 24-week). Our primary analysis will use an intention-to-treat (ITT) analysis that includes all participants who wore the monitor for ≥4 days for 10 hours/day at baseline. The statistical model underlying the analysis a mixedeffects model to examine the main and interaction effects of group (Intervention vs. Control) and time (BL, 12-week) on MVPA (minutes/day). The null hypothesis is that there is no difference in change in MVPA in the Intervention group compared to the Control group. The alternative hypothesis is that there is a difference between groups. The nature of the hypothesis is confirmatory as this study has been powered to detect a difference should one exist. The mixed-effect model will be used to calculate the mean and 95% Confidence Interval time in MVPA at each study time point. We will also calculate the difference in means and 95% Confidence Intervals between the Intervention and Control group at each study time point. We will also calculate 2-sided p-values to determine statistical significance of differences between groups by time in MVPA. Data will be summarized by intervention group. Means, Standard Deviations, Minimums and Maximums will be used to summarize continuous variables. Categorical variables will be summarized as frequencies and percentages.

Mixed-effect modeling will be used to estimate MVPA over time. The mixed-effect model using restricted maximum likelihood estimation is a full information approach and leads to unbiased model parameter estimates in the presence of MCAR or MAR missingness. Selection between models with two common covariance structures, Toeplitz and independent errors, will be accomplished using the Akaike Information Criterion (AIC).

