### 9.5 Primary Efficacy Analysis

The primary endpoint of our study is to examine the efficacy of a physical therapist-delivered exercise intervention (Delaware PEAK, referred to as the Intervention) to increase MVPA over 12 weeks compared to a control group receiving web-based resources about knee OA and exercise (referred to as the Control).

The statistical model underlying this analysis is a mixed-effects model to examine the main and interaction effects of *group* (Intervention vs. Control) and *time* (baseline, 12-week) on MVPA (minutes/day).

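### SAP 8.3 picks covariates from chance baseline differences, and 9.4/9.5 do not say whether they enter the confirmatory MVPA model, so its adjustment is not fixed; the harm is modest and the remedy cheap

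*SAP*

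**What the plan says.** SAP 8.3, with the same wording in Protocol 8.3, compares baseline demographics between the arms after randomization. It then says: "Covariates will be determined based on the presence of group differences". It gives no closed list of candidates, no test or threshold, no form of entry, and no analysis to which the covariates apply.

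The primary model is in SAP 9.4 and 9.5 (Protocol 10 and 10.1). Section 9.5 begins: "The statistical model underlying this analysis is a mixed-effects model to examine the main and interaction effects of" group and time (baseline, 12 weeks) on MVPA. Neither section mentions covariates or refers to 8.3, and neither says that the model is unadjusted. Section 9.4 adds: "The nature of the hypothesis is confirmatory as this study has been powered to detect a difference should one exist".

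Other places bear on the question:

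- SAP 8.4 refers to "each of the three covariates, age, sex and body mass index", but only when looking for patterns of missingness.
- SAP section 15, Tables 2 and 3, show plain means, SDs and mean differences with confidence intervals. Supplemental Tables 4A and 4B are headed as adjusted means and name no adjustment variables.
- SAP 6.3: "Statistical analyses will be performed in a blinded manner".

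**The concern.** Randomization makes every baseline difference between the arms a chance event. A rule that adjusts for whatever happens to differ therefore does not look for predictors of MVPA. At a 5% screen, a strong predictor and a pure noise variable are each picked about 5% of the time. Adjustment earns precision only when the variables are prognostic, and this rule is blind to that.

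The second problem is that the rule is not connected to the model. A reader cannot tell whether 8.3 covariates enter the confirmatory analysis or how. The form of entry matters. In a two-visit model with complete data, covariates entered only as main effects leave the group-by-time contrast essentially unchanged, while covariates entered with time interactions change it. At stake is whether the primary estimate of a test described as confirmatory is defined before the data are seen.

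**Working it through.** **1. Inputs.** The documents give 100 randomized participants (SAP 7), blocks of 4 with no stratification factors (SAP 6.3), two-sided p-values and 95% intervals (SAP 9.4). They give no effect size, SD, power, numerical alpha or dropout, so N = 100 cannot be reproduced. Assumed here: alpha 0.05, 50 per arm, a p<0.05 screen. For scale, the detectable standardized difference at 80% power is (1.960 + 0.842) × √(2/50) = 0.56.

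**2. Chance that the rule picks something.** With m independent candidates screened at level a, the chance is 1 − (1 − a)^m.

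- m = 3 (the age, sex and BMI of SAP 8.4): 1 − 0.95^3 = 14%.
- m = 12 (the characteristics in SAP Table 5, treated as independent): 1 − 0.95^12 = 46%.
- At a = 0.10: 27% and 72%.

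Twelve is the upper end, because weight, height and BMI are linked and correlation lowers the figure.

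**3. Error rates of the rule.** Simulated with N = 100, 12 independent candidates, four of them explaining 0 to 40% of residual 12-week variance, baseline to 12-week correlation 0.3 to 0.9, 4,000 trials per cell:

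| Analysis | Type I error | Power |
|---|---|---|
| No adjustment | 4.4–5.5% | 79.3–80.8% |
| Rule fixed at p<0.05 | 4.3–5.0% | 78.5–80.9% |
| Smallest p of none, 0.05, 0.10, 0.20 | 5.9–7.5% | – |

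A true predictor was selected in 4.3 to 5.5% of trials. The fixed rule's power was 1.6 points below to 0.6 above no adjustment; another run put it 0.9 to 1.9 points below. Other null simulations gave 3.7 to 5.0% for the fixed rule. With only three candidates, the best of four analyses gave 4.8 to 6.2%.

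**4. A separate question: conditioning on baseline MVPA.** The group-by-time contrast compares changes. Baseline MVPA is in that model as an outcome row, but the contrast does not condition on it. Let k be the ratio of the 12-week SD to the baseline SD and r the correlation. Conditioning changes the variance by the factor

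k²(1 − r²) / (1 + k² − 2rk),

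times 95/94 for estimating the slope. Start from 80% power (noncentrality 2.829, 98 df), divide by the square root of the factor, and use 97 df. Example, k = 1 and r = 0.5: the factor is 0.75 × 95/94 = 0.758, noncentrality 2.829/√0.758 = 3.249, power 89.6%.

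| k | r = 0.3 | r = 0.5 | r = 0.7 | r = 0.9 |
|---|---|---|---|---|
| 1.00 | 93.3% | 89.6% | 85.6% | 81.6% |
| 1.15 | 90.1% | 85.8% | 81.7% | 79.8% |
| 1.30 | 87.4% | 83.1% | 79.9% | 82.9% |

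The gain vanishes at k = 1/r (1.43 at r = 0.7). A larger 12-week SD is plausible, since entry excludes those who "Regularly exercise for more than 60 minutes/week" and one arm is meant to become more active.

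**5. Covariance, if baseline means are set equal.** SAP 9.4 plans: "Selection between models with two common covariance structures, Toeplitz and independent errors, will be accomplished using the Akaike Information Criterion (AIC"). At two visits, Toeplitz means one common variance. REML simulations used 3,000 trials per cell, r of 0.5 or 0.7, and 0 or about 15% missing 12-week MVPA:

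- Plan's group-by-time model: type I error 4.2–6.1%.
- Equal baseline means, unstructured covariance: 4.5–6.2% (Monte Carlo SE 0.4 points).
- Equal baseline means, common variance: 4.4–5.1% at k = 1, 6.8–7.4% at 1.15, 7.5–9.0% at 1.3.

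The unstructured version gave the same estimate as ANCOVA in participants with 12-week data. Its power against the plan's model ran from 90.0 v 80.9% (k = 1, r = 0.5, complete data) to 72.0 v 72.6% (k = 1.3, r = 0.7, missing data).

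**The case against.** The best defence is that 9.4 and 9.5 already define an unadjusted model: they list three terms, and the main mock Tables 2 and 3 show unadjusted means and differences. This is the likelier reading, and it narrows the ambiguity. It does not close it. Section 8.3 would then have no stated use. Supplemental Tables 4A and 4B say adjusted without naming variables, which may only mean model-based means, but the SAP does not say so.

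It is also fair that the rule does little direct damage and that the baseline-MVPA point is not caused by 8.3. Group by time is a valid test of the null in 9.4. Preferring a baseline-conditioned contrast is advice about efficiency, and it depends on SDs and correlations that the documents do not give.

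A reader might infer that the rule inflates type I error, or that covariates will be chosen to favour the result. The documents support neither. A fixed screen stays at about 4 to 5%. No passage describes choosing a threshold after seeing outcomes, and blinded analysis limits it. Blinding does not, however, fix the covariate set. A reader might also take age, sex and BMI as a pre-specified adjustment list. SAP 8.4 uses them only for the missingness check.

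**Conclusion.** The point holds as a specification defect of minor to moderate weight. The plan states a selection rule unrelated to prognosis and leaves open whether it touches the confirmatory model. The validity of the group-by-time test itself is not in question.

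The sizes in the working rest on an assumed p<0.05 screen, alpha of 0.05, 50 per arm and independent candidates. Of these, the 5 to 7.5% type I error needs someone to choose the threshold with results in view. The gain from conditioning on baseline MVPA, about 13 points of power to nil from an assumed 80%, is an optional benefit of the repair and not a measure of the defect.

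**What to change.** 1. In 8.3, replace the selection sentence with:

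> Baseline differences between groups do not select covariates for the primary analysis. Any adjustment prompted by an observed imbalance is reported as a sensitivity analysis and labelled as such.

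2. In 9.4 and 9.5, add:

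> The primary model contains no covariates other than baseline MVPA.

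3. As a separate efficiency improvement, make the primary estimate the 12-week group difference conditional on baseline MVPA. Two equivalent forms serve:
   - ANCOVA of 12-week MVPA on group and baseline MVPA.
   - A two-visit REML model with equal baseline means, a group effect at 12 weeks only and unstructured covariance. The covariance is not a common variance and is not chosen by AIC. Baseline MVPA is not also entered as a covariate. Use small-sample degrees of freedom such as Kenward-Roger.

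4. Section 9.4 promises a between-group difference at every time point. Present the baseline comparison descriptively, since a model with equal baseline means does not estimate it.

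The cost is SAP text and analysis code, with no new data. The drawback is a late change of primary estimator. Randomization was expected to finish in December 2022 (SAP Table 4), and version 1.2 is dated 7/2/2024, so on that schedule follow-up has ended. The change must be documented before unblinding. Otherwise keep group by time, with no 8.3 covariates, as primary and report the baseline-conditioned analysis as a labelled sensitivity analysis.

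This does not solve missing data: with two visits, participants without 12-week MVPA add nothing to the contrast. It also leaves for separate settlement the analysis set (all randomized in 8.2.1, baseline wearers in 9.4), the Box-Cox choice in 8.4, and the 24-week and secondary models.
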